5.9.3. Harm monitoring for excess severe COVID-19 cases

Vaccine harm monitoring is intended to monitor for vaccine-induced enhanced disease and will be performed for severe/critical COVID-19 cases based on the FAS each calendar day. Specifically, monitoring for a higher rate of severe/critical disease or death starts at the 5th event, until the harm boundary is reached, or until the primary efficacy analysis is triggered. Monitoring for harm of severe/critical COVID-19 cases will be performed on a daily basis on all available severe cases, irrespective of their analysis ready status. (from Amendment 5 of the SAP, only severe/critical cases as adjudicated by the Clinical Severity Adjudication Committee will be used in the severe harm monitoring).

The monitoring excess severe is done using an exact one-sided binomial test of the null hypothesis $H_0: p \leq 1/2$ versus the alternative hypothesis $H_1: p > 1/2$, where p is the probability that an -infected participant was assigned to the vaccine arm (as opposed to being assigned to the placebo arm). The testing for harm starts at the 5th total severe cases in the FAS and is performed continuously through the primary analysis. Each test is performed at an uncorrected one-sided significance level of $\alpha = 0.05$.

5.9.4. Non-efficacy monitoring

[figure not shown]
The non-efficacy monitoring is based on analysis-ready moderate/severe cases in the FAS, where a participant must be seronegative at baseline to be included in this boundary monitoring. Every effort will be made to establish seronegativity in time. In the unlikely case seronegativity is not

established in time for a case that is to be included in a monitoring calculation otherwise (ie, on Day 14 of an episode), the case will only be included for non-efficacy monitoring at the time seronegativity is established; monitoring calculations will not be repeated at that time.

This boundary will be verified starting once 20 analysis-ready moderate/severe cases in the FAS (seropositive) are observed. From that point onwards, after at least weekly, the boundary will be checked on analysis-ready cases. Monitoring for non-efficacy stops when the primary analysis is triggered. The boundary to be used for non-efficacy is provided in [Table 12](#) and illustrated in [Figure 5](#) , and is based on the case splits that trigger the rules as defined in [Table 10](#) using the methods laid out in Appendix 8 with the exact binomial based confidence intervals.

Table 12 The Number of Confirmed Moderate/Severe Cases on Placebo and Total Number of Confirmed Moderate/Severe Cases at which Point the Non-efficacy Boundary has been Crossed (FAS – seronegative)

Placebo	Total	Placebo	Total	Placebo	Total	Placebo	Total
≤7	20	27	56	47	91	67	126
8	21	28	58	48	93	68	127
9	23	29	60	49	95	69	129
10	25	30	61	50	96	70	131
11	27	31	63	51	98	71	132
12	29	32	65	52	100	72	134
13	31	33	67	53	102	73	136
14	32	34	68	54	103	74	138
15	34	35	70	55	105	75	139
16	36	36	72	56	107	76	141
17	38	37	74	57	108	77	143
18	40	38	75	58	110	78	144
19	42	39	77	59	112	79	146
20	43	40	79	60	114	80	148
21	45	41	81	61	115	81	150
22	47	42	82	62	117	82	151
23	49	43	84	63	119	83	153
24	51	44	86	64	120	84	155
25	52	45	88	65	122	85	156
26	54	46	89	66	124	86	158

Figure 5 Boundary for Non-Efficacy (FAS, seronegative)

5.9.5. Efficacy monitoring

As the efficacy monitoring is linked to the co-primary endpoints, the statistical details on efficacy monitoring are already described in the corresponding section, section 5.4.

Table 13 describes the number of analysis-ready co-primary endpoints required as a fraction of the total number of cases in order to stop and reject the primary study hypotheses, and is illustrated in Figure 6.

[figure not shown]
If the prespecified boundary is met for both co-primary endpoints in the situation that the constraints have also been met (a minimum of 42 molecularly confirmed, moderate to severe/critical COVID-19 cases including 6 in the population of participants aged 60 years or older with onset at least 28 days after double-blind vaccination, a minimum of 5 of molecularly confirmed severe/critical COVID-19 cases in the placebo group with onset at least 28 days after double-blind vaccination with a favorable split for both co-primary endpoints), the SSG will inform the DSMB and, if deemed appropriate by the DSMB, a meeting with the DSMB and the Sponsor Committee will be set up to discuss the efficacy signal. Upon this meeting the Sponsor Committee can trigger internal decision procedures to initiate health authority interactions based on the outcome of the study. If deemed appropriate based on the data, the Sponsor Committee will send the reviewed data package to a designated unblinded team independent of the study team (including a clinician, a statistician, a statistical programmer, and a regulatory person) through a secured medium, who will ensure the complete package meets the requirements for a regulatory interaction and is subsequently transmitted securely to the appropriate regulatory agency. The

sponsor will remain blinded until the data base for the primary analysis is locked or until the time of the snapshot analysis.

Table 13 The Number of Confirmed Moderate/severe Cases on Active and Total Number of Confirmed Moderate/severe Cases at which Point the Efficacy Boundary has been Crossed (PP)

Active	Total	Active	Total	Active	Total
0	20	16	65	32	111
1	22	17	68	33	114
2	25	18	71	34	117
3	28	19	74	35	120
4	30	20	77	36	123
5	33	21	79	37	126
6	36	22	82	38	128
7	39	23	85	39	131
8	42	24	88	40	134
9	45	25	91	41	137
10	48	26	94	42	140
11	51	27	97	43	143
12	54	28	100	44	146
13	56	29	103	45	149
14	59	30	105	46	152
15	62	31	108	49	154

The blinded total number of infections in the FAS with onset of infection after study double-blind vaccination may be monitored to track progress and ensure timely cleaning to facilitate operationalization of data base lock.

Figure 6 Boundary for Efficacy (PP)

5.9.6. Sample size monitoring

The incidence of moderate to severe COVID-19 seen in the US and reported in other COVID-19 vaccine trials is significantly higher than assumed at the time of protocol planning. Furthermore, based on that incidence and modeling there is a high degree of probability that a signal of efficacy meeting the prespecified criteria in the protocol amendment 3 will be reached at or prior to the time when 50% of participants will have been followed for 8 weeks from the time of immunization, therefore the sample size was reduced from 60,000 to approximately 40,000.

5.9.7. Data and Safety Monitoring Board (DSMB)

The study will be formally monitored by a DSMB (also known as an Independent Data Monitoring Committee or IDMC). In general, the DSMB will monitor safety data on a regular basis to ensure the continuing safety of the participants. Enrollment (if applicable) will not be paused during regular safety reviews. The DSMB will review unblinded data. The DSMB responsibilities, authorities, and procedures will be documented in the DSMB Charter and DSMB Charter Addendum.

The DSMB will also review Day 3 safety data (ie, from Day 1 to Day 3; including safety data from the ongoing clinical studies) from participants enrolled in Stage 1a and Stage 2a, before enrollment of participants in Stage 1b and Stage 2b is initiated, respectively. Vaccination of participants in the respective age groups will be paused during these safety reviews.

Continuous monitoring of safety and (non-) efficacy is described in detail in Section 5. If a boundary is met, the SSG immediately informs the DSMB through secure communication procedures. At this point a quorum of the DSMB will be convened as soon as possible and provide a recommendation to the Oversight Group. See also Section 9.8 of the CTP.

5.9.8. Clinical Severity Adjudication Committee

The Clinical Severity Adjudication Committee will review all cases in the study, except for cases already adjudicated as severe, as a supplement to the algorithm described in the SAP, as well as those requiring medical intervention (such as a composite endpoint of hospitalization, ICU admission, mechanical ventilation, and ECMO, linked to objective measures such as decreased oxygenation, X-ray or CT findings), including onset of cases, taking into account all available relevant information at the time of adjudication. More details will be provided in the revised charter of the Clinical Severity Adjudication Committee. Depending on an algorithmic selection the cases will be sent to for adjudication on a case by cases basis or on a sample approach, as explained in section 5.2.1. Re-adjudication will occur if new information becomes available. The last adjudication for a given case will determine the status of the case for analysis. The Clinical Severity Adjudication Committee's assessment will be considered the definitive classification of the case.

6. SUPPORTING DOCUMENTATION

6.1. Appendix 1 List of Abbreviations

ADaM	Analysis Data Model
AE	adverse event
AESI	adverse event of special interest
ATC	anatomic and therapeutic class
BMI	body mass index
CD4	cluster of differentiation 4
CD8	cluster of differentiation 8
CI	confidence interval
CRF	case report form
CTP	clinical trial protocol
DSMB	Data and Safety Monitoring Board
ECG	electrocardiogram
ELISA	enzyme-linked immunosorbent assay
ELISpot	enzyme-linked immunospot
FAS	full analysis set
FDA	Food and Drug Administration
GMC	geometric mean antibody concentration
GMT	geometric mean titer
GSD	group sequential design
HR	hazard ratio
ICF	informed consent form
IDMC	Independent Data Monitoring Committee
IFNg	interferon gamma
IL2	interleukin 2
IRR	incidence rate ratio
ITT	intent-to-treat
LLOQ	lower limit of quantification
NA	not applicable
PBMC	peripheral blood mononuclear cells
PP	per protocol efficacy analysis set
PPI	per protocol immunogenicity analysis set
SAE	serious adverse event
SAP	statistical analysis plan
SD	standard deviation
SDTM	Study Data Tabulation Model
SE	standard error
SFU	spot forming units
SN	seronegative
SP	seropositive
TNE	target number of events
SPRT	sequential probability ratio test
TNF α	tumor necrosis factor alpha
ULOQ	upper limit of quantification
VE	vaccine efficacy
VNA	virus neutralizing antibody
vp	virus particle
WHO	World Health Organization

6.2. Appendix 2 Changes to Protocol-Planned Analyses

SAP according to EDMS-RIM-50860, Amendment 5

History:

SAP Version	CTP Version
1	Initial release
2	SAP according to EDMS-RIM-50860, Amendment 1
3	SAP according to EDMS-RIM-50860, Amendment 2
4	SAP according to EDMS-RIM-50860, Amendment 3
5	SAP according to EDMS-RIM-50860, Amendment 4 and 5

6.3. Appendix 3 Demographics and Baseline Characteristics

The following demographic and baseline characteristics will be summarized.

Table 14 presents a list of the demographic variables that will be summarized by vaccine regimen and overall for the FAS. Demographics will also be summarized by region using the FAS.

Table 14 Demographic Variables

Continuous Variables:	Summary Type
Age ([years])	Descriptive statistics (N, mean, standard deviation [SD], median and range [minimum and maximum]).
Weight (kg)	
Height (cm)	
Body Mass Index (BMI) (kg/m ²)	
Categorical Variables	
Age group 1 (18-≤59, ≥60 years)	
Age group 2 (18-<40, 40-≤59, ≥60 years)	
Age group3 (18-<40, 40-≤59, 60-≤69, 70-≤79, ≥80 years)	
Age group 4 (18-64, ≥65years)	
Age group 5 (≥75years)	
Sex (male, female, unknown, intersex)	
Race ^a (American Indian or Alaska Native, Asian, Black or African American, Native Hawaiian or other Pacific Islander, White, Multiple)	
Ethnicity (Hispanic or Latino, not Hispanic or Latino)	
BMI ([underweight <18.5 kg/m ² , normal 18.5-≤25 kg/m ² , overweight 25-<30 kg/m ² , obese ≥30 kg/m ²])	
Working Status	
Profession	
Breastfeeding (yes, no)	
Frailty index (frail, pre-frail, non-frail, unknown)	

^aIf multiple race categories are indicated, the Race is recorded as 'Multiple'

6.4. Appendix 4 Protocol Deviations

Major protocol deviations and major protocol deviations potentially impacting immunogenicity or efficacy (see section 4) will be summarized.

In general, the following list of major protocol deviations may have the potential to impact participants' rights, safety or well-being, or the integrity and/or result of the clinical study. Participants with major protocol deviations will be identified prior to data base lock and the participants with major protocol deviations will be summarized by category.

[Developed withdrawal criteria but not withdrawn]

[Entered but did not satisfy criteria]

[Received a disallowed concomitant treatment]

[Received wrong treatment or incorrect dose]

[Other]

6.5. Appendix 5 Prior and Concomitant Medications

The analysis of concomitant therapies will be done using the WHO drug coded terms.

For all participants, concomitant therapies associated with an SAE will be collected and recorded in the eCRF from the moment of vaccination through the end of the study. Concomitant therapies associated with MAAEs will be collected and recorded in the eCRF from the moment of double-blind vaccination until 6 months after double-blind vaccination. Concomitant therapies associated with MAAEs leading to study discontinuation will be recorded in the eCRF during the entire study. The proportion of participants with concomitant medication associated with these SAEs and MAAEs will be tabulated with exact 95% CI.

For all participants, concomitant therapies associated with COVID-19 will be captured in the electronic eCRF for the duration of the study. The proportion of participants with new concomitant medication associated with these cases will be tabulated with exact 95% CI. New concomitant medications are defined as medications not available at baseline or medication with an increased dosage (See below, New Concomitant Medications, for details), compared to baseline. Baseline medications are all medications reported prior to and at the day of double-blind vaccination. In case a baseline medication is reported multiple times then only the last available record reported prior to or at the day of double-blind vaccination will be used.

For participants in the Safety Subset, concomitant therapies associated with unsolicited AEs will be collected, recorded in the eCRF from the time of double-blind vaccination through 28 days after double-blind vaccination and the proportion of participants with concomitant medication will be tabulated with exact 95% CI. Concomitant therapies associated with solicited AEs will be collected by the participants, recorded in the eCRF from the time of double-blind vaccination through 7 days after double-blind vaccination and the proportion of participants with concomitant medication will be tabulated with exact 95% CI.

Based on their start and stop date, concomitant therapies will be reported in each applicable phase.

If a concomitant therapy record misses components of its start and/or stop dates (time, day and/or month and/or year):

In case of partial start or stop dates, the concomitant therapy records will be allocated to periods using the available partial information, without imputations. If, for example, only month and year are available, these will be compared to the month and the year of the periods, and the concomitant therapy record will be allocated to the period(s) where these date parts match. This rule may lead to assignment to multiple periods. In case it is clear the medication was taken after vaccination, the start will be allocated to the correct phase without the use of the start dates (time, day and/or month and/or year). In case of a completely missing end date, the concomitant therapy will be considered as ongoing at the end of the trial.

There will be special attention to any systemic use of analgesics/antipyretics, started during 8 days following each vaccination (00:00 of day of vaccination + 7 days). Following CMCLASCD (ATC/DD codes) will be used for this: N02A (OPIOIDS) and N02B (OTHER ANALGESICS

AND ANTIPYREtics), M01A (ANTIINFLAMMATORY AND ANTIRHEUMATIC PRODUCTS, NON-STERoIDS) and M01B (ANTIINFLAMMATORY/ANTIRHEUMATIC AGENTS IN COMBINATION). The classes will be added in a footnote in all related tables and listings. For the use of analgesics/antipyretics which are taken on the day of vaccination an exception is made in case the time is before vaccination. In this case the concomitant medication is also allocated to the post-dose period.

Additionally, safety data will be presented for subjects that uses corticosteroids.

New Concomitant Medications – Increase in dosage Calculation

In case a participant receives the same medication with the same form at baseline and during an COVID-19 episode, then in order to identify whether there was an increase in dose between baseline and the episode the medication dose will be calculated by multiplying the dosage per administration with the number of administrations per day or per week, as applicable for both timepoints and compared.

This rule applies for the following medication frequencies:

- Once weekly (1 time per week)
- Twice weekly (2 times per week)
- Three Times weekly (3 times per week)
- Four Times weekly (4 times per week)
- Twice Daily (BID)
- Twice per Month (BIM)
- Every two weeks (Every 2 weeks)
- Every four weeks (Every 4 weeks)
- Weekly (Every week)
- Once
- Per Year
- Every three months (Q3M)
- Daily (QD)
- Four times daily (Q1D)
- Monthly (QM)
- Every Other Day (QOD)
- Three times daily (TID)

For frequencies equal to ‘other’ at baseline, any change to one of the above frequencies will be considered an increase, given that the form remains the same. For frequencies equal to ‘as necessary’ (PNR) or ‘occasional’, any change to another frequency or dose will be considered as

an increase. A change from 'as necessary' (PNR) to 'occasional' or 'other' will not be considered as an increase.

Moreover, capsule and tablet are considered the same form so to define if there was an increase the dose and the frequency will be used as defined above. The same applies for inhalant and aerosol.

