5.1.1. Study Phases

A baseline (or reference) value will be defined as the value of the last available assessment prior to the vaccination on Day 1.

The safety analysis will present all results by study phase (see Section 5.1.2). Immunogenicity results will be presented per scheduled time point as appropriate. Listings will be shown per phase and time point.

Study day or relative day is defined as follows:

- Study Day = visit date – date of Day 1 + 1; if visit date \geq date of Day 1 (date of first vaccination).
- Study Day = visit date – date of Day 1; if visit date $<$ date of Day 1 (date of first vaccination).

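### Two Appendix 5 rules for new medication in COVID-19 episodes misclassify some records: reductions from as-needed use count as increases, and a drug started after the injection on Day 1 can become baseline

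*SAP*

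**What the plan says.** All the rules are in SAP section 6.5 (Appendix 5), except the general baseline definition in section 5.1.1.

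- **Definition of new.** "New concomitant medications are defined as medications not available at baseline or medication with an increased dosage" The proportion of participants with such medication linked to their COVID-19 episode is tabulated with an exact 95% interval.
- **Listed frequencies.** For the same drug and form, the dose is obtained by "multiplying the dosage per administration with the number of administrations per day or per week, as applicable for both timepoints and compared".
- **As-needed or occasional at baseline.** "any change to another frequency or dose will be considered as" an increase. One exception follows: a move from as-needed to occasional or other "will not be considered as an increase".
- **Other at baseline.** "any change to one of the above frequencies will be considered an increase, given that the form remains the same".
- **Baseline medication.** "Baseline medications are all medications reported prior to and at the day of double-blind vaccination". If a drug was reported more than once, the last such record is used.
- **General baseline (section 5.1.1).** The "value of the last available assessment prior to the vaccination on Day 1".

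**The concern.** The definition of new medication turns on an increase, but the rules that implement it for as-needed, occasional and other use do not ask whether anything went up. As-needed use is a common pattern for analgesics and antipyretics, so this is not a remote case.

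The baseline rule works by calendar day. An antipyretic taken on the evening of Day 1 for a reaction to the injection is a post-vaccination record, yet it can serve as the baseline against which the episode is judged. If the same drug recurs at the same dose during COVID-19, it is no longer new. If a true pre-vaccination record exists, the later one replaces it.

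At stake is how many cases in each arm are shown as having started or stepped up medication. The exact interval reflects sampling error only and carries no allowance for records misclassified by rule.

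**Working it through.** The SAP states no figure for this table, so there is none to reproduce. The check applies the rules literally, compares the baseline definitions, and then bounds the possible arm difference.

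**1. The increase rules applied to test records.** The doses are illustrative only.

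| Baseline | Episode | Result as written | What actually changed |
|---|---|---|---|
| As-needed 1000 mg | As-needed 500 mg | Increase | Dose per administration halved |
| As-needed 500 mg | As-needed 1000 mg | Increase | Dose per administration doubled |
| As-needed 1000 mg | Weekly 500 mg | Increase | Dose halved; baseline intake unknown |
| Occasional 1000 mg | As-needed 500 mg | Increase | Dose halved; change in frequency not quantified |
| Other 1000 mg | Weekly 250 mg | Increase | Dose quartered; baseline frequency unknown |
| As-needed 1000 mg | Occasional 500 mg | Not an increase | Covered by the exception |
| Daily 500 mg | Daily 250 mg | Not an increase | Dose halved |
| Daily 500 mg | As-needed 500 mg | No rule applies | Direction unknown |

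The first and seventh rows show the inconsistency: the same halving is an increase from as-needed use and not an increase from daily use. The last row is a gap, because no rule covers a listed frequency changing to as-needed.

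**2. The baseline definitions side by side.** Section 5.1.1 stops before the vaccination. Appendix 5 runs to the end of the vaccination day and takes the last record. Appendix 5 also places analgesics and antipyretics from the day of vaccination in the post-dose period, even when taken before the injection. A same-day analgesic can therefore be a baseline medication for one output and a post-dose medication for another.

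**3. Possible arm difference from the Day 1 rule.** Difference = p × s × m × (a_v − a_p), where:

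- p = true proportion of cases with a new medication: 50% (assumed).
- s = share of participants whose Day 1 reactogenicity drugs are systematically recorded. Appendix 5 collects therapies for solicited events in the Safety Subset, about 6,000 participants (section 3.4), out of about 40,000 (section 3.1): 6,000/40,000 = 15%.
- a_v, a_p = shares starting a drug after the injection on Day 1, vaccine and placebo: from 10% versus 2% up to 30% versus 5% (assumed).
- m = probability that the same drug and form recurs in the episode with no counted increase: 10% to 50% (assumed).

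Low: 0.50 × 0.15 × 0.10 × (0.10 − 0.02) = 0.0006, or 0.06 points.

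High: 0.50 × 0.15 × 0.50 × (0.30 − 0.05) = 0.0094, or 0.94 points.

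If such drugs were recorded for everyone (s = 100%), the range would be 0.4 points (0.50 × 0.10 × 0.08) to 6.3 points (0.50 × 0.50 × 0.25).

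**4. Scale.** The last row of the efficacy boundary (section 5.9.5, Table 13) is 49 vaccine cases of 154, leaving 105 on placebo. With a proportion near 50%, the exact 95% interval is about 34% to 64% for 49 cases and 40% to 59% for 105.

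**The case against.** The strongest reply is that this is a descriptive table with no hypothesis, and that a specific definition of baseline medication may displace the general one in section 5.1.1, which concerns assessed values. The post-dose placement of same-day analgesics also serves a different output and is itself a calendar-day convention. All of that is fair. It reduces the mismatch to an inconsistency, but a post-injection record still acts as baseline in a table for a randomised trial. For frequency other, direction often cannot be derived, so scoring an increase is a convention; it still asserts a direction that the data do not show.

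Two stronger readings are tempting, and the SAP does not support them.

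- **That the table is tilted by arm.** The as-needed, occasional and other rules are the same in both arms, and true pre-vaccination use is balanced by randomisation. Only the Day 1 rule could differ by arm, and only if post-injection drug use does. That is plausible against saline, but the SAP gives no rates. Masking also needs the same drug and form to recur without a counted increase. Where the Day 1 record is as-needed, the over-broad as-needed rule counts most changes as new anyway, so the two defects partly offset. A participant with any other new drug may still be counted.
- **That doses are compared without a common unit**, for example 10 mg daily against 70 mg weekly as 10 against 70. The phrase *as applicable for both timepoints* is naturally read as one shared unit, and listed frequencies such as every three months cannot be handled without conversion. Stating the unit would help, but no error is established.

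**Conclusion.** The point holds as a minor one. Read literally, Appendix 5 counts some reductions as increases, contrary to its own definition of new medication, and it lets a drug started after the injection on Day 1 become or overwrite the baseline record, which does not fit section 5.1.1. The first rule wrongly adds records to the new category in both arms. The second can remove records from it.

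The overall size is unknown, because the SAP does not say how common these patterns are, and is probably small. A difference between arms is possible through the Day 1 rule but not shown. The 0.06 to 0.94 point range rests on assumed drug-use and recurrence rates and on recording in about 15% of participants, and it is well inside the sampling error of the table. Nothing here reaches the co-primary or confirmatory secondary analyses.

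**What to change.** Amend the Appendix 5 derivation as follows.

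1. Count an increase only when the derived dose or frequency actually rises. A lower as-needed dose that stays as-needed is then not new.
2. Put changes whose direction cannot be derived in a separate undetermined category and tabulate it beside the new category. These are moves from other; as-needed to scheduled use where as-needed intake is unknown; a listed frequency to as-needed; and records with frequency once, which has no daily or weekly rate. As-needed to scheduled use should not be scored automatically as an increase, since one scheduled dose a day can be less than several as-needed doses.
3. Restrict baseline medication to records starting before the date and time of double-blind vaccination, and state what happens when a Day 1 start time is missing. For example, use other evidence that the drug was taken before or after the injection, and otherwise classify the record as undetermined.

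The cost is appendix wording and a revised derivation, with no new data collection. The downside is that some records move to undetermined, so the tabulated proportions become somewhat less complete.
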